# 6.2.7 Analysis of ICU rate, in-hospital mortality and 29 day mortality

The goal is to compare ICU rate and mortality between randomized arms. We will use the same approach as above for the primary outcome (respiratory failure rate).

# 6.3 Adaptive trial design

During the conduct of this trial, new data may emerge to support the clinical and/or antiviral efficacy of an anti-COVID therapy such that this therapy becomes a standard of care. Should this occur, the sample size will be recalculated taking into account the anticipated effect size of the new therapy and any data to inform the anticipated additive or synergistic effect of the therapy when coadministered with CCP. This therapy will be incorporated into the study as soon as possible as the background standard of care, with an expanded sample size as appropriate.

# 7 HUMAN SUBJECTS PROTECTIONS

# 7.1 Risks and Benefits

Potential Benefits of Treatment: The potential benefits of antiviral treatment with anti-SARS CoV-2 plasma in patients with COVID-19 and respiratory symptoms consistent at high risk for respiratory decompensation are not known. We hypothesize that treatment will decrease the risk of disease progression requiring supplemental oxygen, ICU admission and aggressive respiratory support including possible mechanical ventilation (and other ICU support).

Potential Benefits of Clinical monitoring and Virologic Testing: Monitoring and testing are required to assess the effect of convalescent plasma on the course of COVID-19 respiratory disease.

#### 7.1.1 Potential risks

- 1. Risks of Plasma: Fever, chills, rash, headache, serious allergic reactions, TRALI, TACO, transmission of infectious agents
- 2. Risks of Phlebotomy: local discomfort, bruising, hematoma, bleeding, fainting,
- 3. Total blood draws will not exceed 500 mL
- 4. Risks of oropharyngeal and throat swab: local discomfort, vomiting, coughing

Alternatives: The alternative to participation in this study is routine care.

#### 7.1.2 Safety measures

- 1. Safety Evaluations will assess for clinical and laboratory indices of reactions to high antibody level anti-SARS-CoV-2 plasma and determine if they are higher, lower or the same as standard plasma
- 2. Clinical evaluations: Vital signs and symptom screen on days 1-8, 15 and symptom screens on days 29, and 120.
- 3. Laboratory evaluations to include chest radiography (chest x-rays and/or chest CT and/or ultrasound)
- Safety laboratory tests (ABO typing, pregnancy testing, CBC, CRP, and comprehensive metabolic panel) will be performed at the local CLIA-certified clinical laboratory on days 1-8 and 15 as specified by above plan.

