# 6 STATISTICAL PLAN

#### 6.1 Sample Size and Power Considerations

All power calculations were performed using Stata "power" package assuming a two-tailed  $\alpha$ =0.05. The planned sample size for the trial is 50 subjects, randomized in a 1:1 ratio to anti-SARS-CoV-2 convalescent plasma versus control plasma. The primary analysis will compare the combined endpoint of mechanical ventilation or death in the anti-SARS-CoV-2 convalescent plasma and control groups.

We base our sample size projection on the ACTT-1 data [22]They reported the progression within 15 days separately for COVID-19 hospitalized requiring supplemental oxygen and those requiring high flow oxygen or non-invasive ventilation. The proportion progressing were 20% and 34%, respectively in the standard of care group and 8% and 25% in the remdesivir group progression. For our assumption we assume a 32% progression rate on the standard of care (no convalescent plasma) In the absence of treatment with convalescent plasma, we anticipate that between 10 to 30% will experience the primary outcome of mechanical ventilation or death . Using the Fisher exact test: we will reject the null hypothesis under the data scenario in the Table below.

No. Mechanical ventilation/Death (%)	Control arm (%)	Active arm (%)
	5/25 (20%)	0/25 (0%)
	6/25 (24%)	<= 1/25 (4%)
	7/25 (28%)	<= 1/25 (4%)
	8/25 (32%)	<= 1/25 (4%)
	9/25 (36%)	<= 2/25 (8%)
	10/25 (40%)	<= 3/25 (12%)

Rejection Region for the Fisher Exact Test

We will use an 8-point ordinal scale to assess clinical status, based on WHO clinical trial guidance. We assume the same distribution of outcomes for the control arm (i.e., in the absence of treatment with

convalescent plasma) as in ACTT, as tabulated below. Assuming 25 participants are treated with convalescent plasma and 25 participants are untreated, we would have 80% power to detect a difference between treatment arms as follows:

Category	Control arm (%)	Active arm (%)
Death	12%	0
Hospitalized, on invasive mechanical ventilation plus additional organ support (pressors, RRT, ECMO)	0	0
Hospitalized, intubated and mechanical ventilation	20.0%	0
Hospitalized, on non-invasive ventilation or high flow oxygen devices;	12%	8%
Hospitalized, requiring supplemental oxygen fy mask or nasal prong	0	20%
Hospitalized, not requiring supplemental oxygen – requiring ongoing medical care (COVID-19 related or otherwise);	24%	12%
Not hospitalized, limitation on activities	16%	28%

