# 6.2 Statistical Analysis

# 6.2.1 **Primary endpoint**

Our primary hypothesis is that by providing anti-SARS-CoV-2 plasma, the rate of progression to mechanical ventilation or death will be decreased as compared to the rate in in the group receiving control plasma. We will apply a Fisher exact test to compare the combined endpoint of mechanical ventilation/death respiratory failure rates between the two groups occurring by day 15. 29. All analyses

will be conducted with a modified intention-to-treat approach, which excludes randomized subjects who do not initiate an infusion of the study plasma. As secondary analysis, we will also analyze the reduced oxygenation rate, requirement for supplemental oxygen rate, length of hospitalization, time to recovery (ordinal score 1-3) and mechanical ventilation rate, respectively, as well as occurrence of the primary endpoint by day 29 Statistical inference will be based on a two-sided Type 1 error rate of 0.05 and 95% confidence intervals.

Participants who are intubated for reasons other than hypercarbia/hypoxia, such as for a procedure or airway obstruction, will have ventilation settings evaluated to determine if need for ventilation due to hypoxia is meet. This will be determined by >12 hours of requirement for a mandatory mode of ventilation (volume control or pressure control) or Fi02 of > 40%. External adjudication of intubation for non-hypoxic/hypercarbic indication will be conducted.

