# 6.2.4 Analysis of AE data

Analysis of AE data will primarily be descriptive based on DAIDS toxicity table coding of events. Rates of AE will be compared between randomized arms using Fisher's Exact Test.

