# 6.2.5 Analysis of the anti-SARS-CoV-2 levels and inflammatory markers.

Analysis of antibody levels will primarily be descriptive, comparing the geometric mean antibody levels at days 1,2,5,8,15, 29, and 120 between the randomized arms. Furthermore, it is of interest to describe the entire distributions of anti-SARS-CoV-2 antibody levels by randomized arms and contrast these distributions. Therefore, we will use quantile regression in order to describe whether there is a shift or change in the titer distribution between randomized arms. Given that repeated measures of antibody levels will be obtained, we will account for the correlation in measures within individuals using a cluster bootstrap

33

in order to properly estimate the p-value and 95% confidence intervals. Similar analysis will also be applied to lymphocyte counts on days 1,2,5,8,15, 29 hematological measurements (D-dimer, ferritin, hsCRP) on days 1,2,5,8,15, 29, 29, and other lab measures showing right-skewed distributions. Exploratory analyses of antibody isotypes, neutralizing antibody activity, antibody affinity, glycosylation and T-cell responses will be conducted to compare between arms and over time.

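### Section 7.1.2 promises to say whether reactions are higher, lower or the same, but the only method for adverse event rates, Fisher's test at 25 per arm without a margin or interval, cannot show sameness

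*Combined protocol and SAP*

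**What the plan says.** Section 7.1.2 sets the scope: "Safety Evaluations will assess for clinical and laboratory indices of reactions to high antibody level anti-SARS-CoV-2 plasma". The purpose it states for this is to "determine if they are higher, lower or the same as standard plasma". No margin that would define sameness is given there or elsewhere.

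Section 6.2.4 gives the AE analysis in two sentences. The first reads "Analysis of AE data will primarily be descriptive based on DAIDS toxicity table coding of events". The second reads "Rates of AE will be compared between randomized arms using Fisher's Exact Test". Neither mentions an estimate of the between-arm difference or an interval for it.

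Three other passages bear on the point:
- Section 6.2.5 compares laboratory measures (lymphocyte counts, D-dimer, ferritin, hsCRP and other right-skewed measures) in the same way as antibody levels, for which "we will use quantile regression in order to describe whether there is a shift or change in the titer distribution between randomized arms". Bootstrap p-values and 95% intervals are planned, but no margin.
- Section 6.2.3 gives by-arm percentages with 95% intervals for binary secondary data, and odds ratios with intervals for categorical data. AEs have their own section and are not among its examples.
- The objectives tables (sections 3 and 5.1) ask for safety relative to control through serious AEs, Grade 3 and 4 AEs and transfusion-associated events. They claim neither equivalence nor non-inferiority.

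**The concern.** Section 7.1.2 offers three possible conclusions. Fisher's test can support higher or lower. Failing to reject equality is not evidence for equality, and without a margin or an interval nothing else in 6.2.4 can supply that evidence. One of the three stated conclusions is therefore out of reach for AE rates.

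At stake is what the trial may say about safety at its close. Safety relative to control is a stated secondary objective, and section 4.1.9 plans to pool the data with similar trials, where an estimate with its uncertainty is more useful than a p-value.

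**Working it through.** **Inputs from the documents.** Size and allocation (6.1): "The planned sample size for the trial is 50 subjects, randomized in a 1:1 ratio", so 25 per arm. Error rate (6.2.1): "Statistical inference will be based on a two-sided Type 1 error rate of 0.05 and 95% confidence intervals". Analysis set (6.2.1): it "excludes randomized subjects who do not initiate an infusion of the study plasma", so the analysed number could fall below 25 per arm. Section 5.3.3 says randomized subjects who withdraw are replaced, but the net effect on the analysed number is not stated. I use 25 throughout.

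**Assumptions.** The documents give no AE rates for the between-arm comparison. The only rate quoted for convalescent plasma is below 1% in the day after infusion, from a background series (4.1.2). All true rates below are mine, for illustration.

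**Step 1: the plan's own figures for this test.** No power, margin or precision is stated for safety. The one published figure for Fisher's test at this size is the rejection table for the primary endpoint in 6.1. The two-sided p-values (control v active events of 25) are:
- 5 v 0: 0.0502
- 6 v 1: 0.098
- 7 v 1: 0.0488
- 8 v 1: 0.0232
- 9 v 2: 0.0374
- 10 v 3: 0.0507

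Three of the six rows reject at 0.05. That mismatch is a separate matter, but 5 v 0 should not be taken from that table as a rejection.

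**Step 2: smallest excess that rejects.** With zero events in one arm and k in the other, the two-sided p-value is 2 × C(25,k) / C(50,k).
- k = 5: 2 × 53,130 / 2,118,760 = 0.0502, not significant.
- k = 6: 2 × 177,100 / 15,890,700 = 0.0223, significant.

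An observed 20% against 0% is therefore declared non-significant.

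**Step 3: what an interval shows for the same counts.** Newcombe's interval for p1 − p0 combines the Wilson limits (l, u) of each arm:
- lower = (p1 − p0) − √[(p1 − l1)² + (u0 − p0)²]
- upper = (p1 − p0) + √[(u1 − p1)² + (p0 − l0)²]

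Wilson 95% limits are 0 to 0.133 for 0/25, 0.022 to 0.250 for 2/25 and 0.089 to 0.391 for 5/25.
- 5 v 0: lower = 0.20 − √(0.111² + 0.133²) = 0.026; upper = 0.20 + 0.191 = 0.391. The excess lies between about 3 and 39 points.
- 2 v 2: ±√(0.058² + 0.170²) = ±0.179, about ±18 points.
- 0 v 0: ±0.133, about ±13 points.

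Even identical counts leave excesses of 13 to 18 points open.

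**Step 4: power under assumed rates.** Power is the sum, over all pairs (x, y) with two-sided Fisher p ≤ 0.05, of Bin(x; 25, p0) × Bin(y; 25, p1).
- 8% v 24%: 0.218
- 20% v 40%: 0.231
- 10% v 20%: 0.086
- 0% v 20%: 0.383

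For the two pairs with a true 20-point excess, the test misses it 77% of the time (20% v 40%) and 62% of the time (0% v 20%).

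**The case against.** Four points can fairly be made for the plan.

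- **The AE analysis is labelled primarily descriptive.** This stands. The fault is an over-worded aim in the human-subjects section, not a formal equivalence claim. But 6.2.4 then names a test and no estimate of the difference, and descriptive intent is better served by the estimate.
- **Fisher's test is not the only safety comparison.** This stands. The aim in 7.1.2 includes laboratory indices, and 6.2.5 compares several of them with intervals. The point is therefore confined to AE rates. Section 6.2.5 has no margin either, so it does not establish sameness for the laboratory measures.
- **Intervals may already be planned through 6.2.3.** Safety is listed among the additional secondary objectives, so the by-arm intervals or odds ratios might be meant to cover AEs. The text does not say so.
- **Low power for safety is usual in a 50-patient proof-of-concept trial, and the fix does not raise it.** True. The change improves what is reported and claimed, not what can be detected.

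A reader might go further and infer that null AE tests will be reported as equal safety, giving false reassurance about antibody-mediated enhancement of infection. The documents do not support this. No passage equates a non-significant test with sameness. Enhancement could also appear as clinical worsening or viral persistence, which are analysed separately: the primary endpoint (6.2.1), the ordinal scale (6.2.2), viral RNA (6.2.6), and ICU rate and mortality (6.2.7). The safety committee's unblinded review (7.4.1) and the halting criteria (8.1) do not depend on Fisher significance, though neither is a test of sameness.

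**Conclusion.** The point holds for AE rates. Section 7.1.2 names a conclusion that the method in 6.2.4 cannot deliver with 25 per arm, no margin and no interval. The p-values and intervals follow from the planned size alone. The power figures, 9% to 38%, rest on assumed rates. Fewer than 25 analysed per arm would generally make precision worse.

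This is a matter of reporting and wording that should be corrected. It does not affect the sample size, conduct or primary inference, and it is not evidence that the trial intends to claim equivalence.

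**What to change.** - **Section 6.2.4:** alongside Fisher's test, report the between-arm risk difference with a 95% score-based interval (Newcombe or Miettinen-Nurminen, chosen in advance) for serious AEs, Grade 3-4 AEs and transfusion-associated AEs. For each, state the largest excess the data do not exclude. Because the interval and Fisher's test can disagree near the boundary, as at 5 v 0, say that both will be shown and that the interval carries the interpretation.
- **Section 7.1.2:** replace the three-way determination with an aim to describe and estimate the difference from standard plasma, and state that a non-significant test will not be reported as equal safety.

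The cost is one extra column in the AE tables, a short wording change and a more modest safety claim. No additional patients or data are needed.

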# 7.2 Definitions

1. **Adverse Event (AE):** Any untoward medical occurrence in a clinical investigation subject who has received a study intervention and that does not necessarily have to have a causal relationship with the study product. An AE can, therefore, be any unfavorable and unintended sign (including an abnormal laboratory finding, for example), symptom, or disease temporally associated with the use of the study product, whether or not considered related to the study product.

2. Serious Adverse Event (SAE): Any adverse event that results in any of the following outcomes:

- 1. Death
- 2. Life-threatening (immediate risk of death)
- 3. Prolongation of existing hospitalization
- 4. Persistent or significant disability or incapacity

5. Important medical events that may not result in death, be life threatening, or require intervention or escalation of care may be considered a serious adverse event when, based upon appropriate medical judgment, they may jeopardize the subject and may require medical or surgical intervention to prevent one of the outcomes listed in this definition. Examples of such medical events include allergic bronchospasm requiring intensive treatment in an emergency room or at home, blood dyscrasias or convulsions that do not result in inpatient hospitalization.

- 3. **Unexpected Adverse Event (UAE):** An adverse reaction, the nature or severity of which is not consistent with the investigator's brochure.
- 4. Serious and Unexpected Suspected Adverse Reaction (SUSAR): An adverse reaction, the nature of which is not consistent with the investigator's brochure with severity as defined by SAE above.
- 5. Unanticipated Problem (UP): Unanticipated Problem that is not an Adverse Event (e.g. breaches of confidentiality, accidental destruction of study records, or unaccounted-for study drug).
- 6. **Protocol Deviation:** Deviation from the IRB-approved study procedures. Designated serious and nonserious
- 7. Serious Protocol Deviation: Protocol deviation that is also an SAE and/or compromises the safety, welfare or rights of subjects or others

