# 4.1.4 **Target population**

This study will enroll hypoxic hospitalized COVID-19 patients, a group that is at elevated risk for poor outcomes and progressive respiratory failure. To date, approximately 30-50% of hospitalized San Francisco COVID-19 patients have required intensive care level treatment, the majority due to respiratory failure[1]. This high progression to ICU level care due to respiratory failure has been seen across the US. This study targets patients who are still early in the course of disease, when CCP may be most effective, the "green zone" described in Figure 2. Once severe respiratory decompensation and ARDS occur and patients have progressed to the "red zone", CCP may be less effective, as was the case with use of CCP in SARS-1 -[8]. The study has been amended to include those on high flow nasal oxygenation, as well as those on nasal cannula. In the ACTT-1 study, 25% of participants on HFNC (ordinal group 6) progressed to mechanical ventilation or death [22] These individuals are at elevated risk of progression to intubation and it is important to understand if CCP can reduce deterioration of respiratory status.

This study will permit enrollment of pregnant women, breastfeeding women and women of childbearing potential. CCP should not pose a pregnancy specific risk, other than the known risks associated with blood product infusions in general. However, for pregnant or breastfeeding women, additional counseling will be provide as to the lack of data for CCP use in COVID-19 infection during pregnancy and lactation and that an adverse event that impacts the participant could also affect an unborn child by affecting maternal health. Pregnant women who chose to enroll will have the pregnancy outcome recorded.

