#### 5.3.2 Exclusion Criteria

1. Contraindication to transfusion due to inability to tolerate additional fluid, such as due to decompensated congestive heart failure

2. Baseline requirement for oxygen supplementation prior to COVID-19 infection or use of positive pressure therapy for sleep disordered breathing

- 3. Currently experiencing severe hypoxemic failure, as defined in study endpoints
- 4. Prior receipt of plasma products, IVIG, or hyperimmune globulin within past 3 months
- 5. Currently enrolled another interventional clinical trial of COVID-19 treatment.

Note: If taking medications with potential anti-COVID activity that do not have data to support efficacy, such as IL-6 antagonists, these medications must be stopped prior to enrollment. Receipt of current standard of care COVID-19 treatment, including remdesivir is permitted and should be recorded as a concomitant medication.

Note: Pregnancy is not exclusionary but will merit additional discussion of risks & benefits in the context of ongoing pregnancy

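### Pregnancy outcome is to be recorded, but no SAE criterion, visit item, reporting route or analysis carries a birth defect or an illness confined to the newborn

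*Combined protocol and SAP*

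**What the plan says.** On eligibility, section 4.1.4 states: "This study will permit enrollment of pregnant women, breastfeeding women and women of childbearing potential". Section 5.3.2 agrees: "Pregnancy is not exclusionary but will merit additional discussion of risks & benefits in the context of ongoing pregnancy". Section 4.1.4 also tells investigators to counsel that "an adverse event that impacts the participant could also affect an unborn child by affecting maternal health", and it makes one commitment on data: "Pregnant women who chose to enroll will have the pregnancy outcome recorded".

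On definitions, section 7.2 describes an adverse event as "Any untoward medical occurrence in a clinical investigation subject who has received a study intervention". An SAE is an adverse event with one of five outcomes: death, immediate threat to life, a longer stay for a patient already in hospital, "Persistent or significant disability or incapacity", or an important medical event. The last applies when, on medical judgment, such events mean that "they may jeopardize the subject and may require medical or surgical intervention to prevent one of the outcomes listed in this definition". Congenital anomaly and newborn harm are not listed.

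On timing, the objectives tables (Protocol Summary and 5.1) count SAEs and Grade 3 and 4 events up to Day 29. The Schedule of Evaluations ends at Day 120, with a window of 14 days either side. Section 7.4.1 has the SMC meet monthly until enrollment is complete.

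**The concern.** The protocol accepts that a fetus may be affected and undertakes to record the pregnancy outcome, but nothing downstream turns that into a working procedure. Table 1 and the day-by-day lists in 5.4 contain a pregnancy test at screening and no later pregnancy item. The AE analysis (6.2.4), the reporting interval (7.3.1) and the monitoring plan (7.4.1) do not mention it.

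The definitions add a second gap. An SAE must first be an AE, an AE must occur in a treated subject, and the important-medical-event item also refers to the subject. A malformation, or an illness affecting only the baby, fits none of these. Staff who follow 7.2 as written would leave it unclassified.

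At stake is a safety signal from exposed pregnancies in either arm. No efficacy result is affected.

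**Working it through.** The plan gives no figure on this point, so there is nothing to reproduce. The check has two parts.

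**1. Which outcomes the definitions reach**

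- *Miscarriage, stillbirth, preterm labour, obstetric complications.* These happen in the mother, who is the subject, so they can be AEs. They are serious if they threaten her life, lengthen her current stay, or are judged important medical events. Once classed as AEs or SAEs that 7.3.1 requires to be documented, they are followed to resolution, even past the reporting period. One weakness is that the hospitalization item covers only a stay already in progress, so an obstetric readmission after discharge would need another item to count as serious.
- *Congenital anomaly, or illness confined to the newborn.* No item applies. The follow-to-resolution rule does not help, because it starts only once something has been classed as an AE or SAE.
- *SAEs learned of after the study.* The relevant sentence in 7.3.1 sets up the condition and then stops without stating an action. It also relies on the same SAE definition.

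**2. When delivery falls relative to the cut-offs**

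Inputs from the documents: Day 29 for the SAE comparison, and Day 120 (plus up to 14 days) for the last visit. The documents give no length of gestation, so I assume a 280-day term with a range of 259 to 294, and infusion on Day 1. Day d is then d − 1 days after infusion. Delivery falls after Day d when gestational age at infusion is below

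threshold = term − (d − 1).

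| Cut-off | Days after infusion | Term 259 | Term 280 | Term 294 |
|---|---|---|---|---|
| Day 29 | 28 | 231 d = 33w0d | 252 d = 36w0d | 266 d = 38w0d |
| Day 120 | 119 | 140 d = 20w0d | 161 d = 23w0d | 175 d = 25w0d |
| Day 120 + 14 | 133 | 126 d = 18w0d | 147 d = 21w0d | 161 d = 23w0d |

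For illustration only, suppose gestational age at infusion is spread evenly over 280 days. The share delivering after Day 29 is then 252/280 = 90%, after Day 120 it is 161/280 = 57.5%, and after Day 134 it is 147/280 = 52.5%. If 0 to 3 of the 50 participants were pregnant (an assumption), 57.5% of them is 0 to 1.7 women.

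Day 29 is the tighter limit. It excludes nearly all births except those after infusion close to term.

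**The case against.** The best counter-argument is that several routes remain open:

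- The undertaking in 4.1.4 has no time limit, and 9.6.1 allows data to be abstracted from medical records. A delivery after Day 120 could therefore be recorded without a study visit.
- A recorded outcome is trial data, and 7.4.1 gives the SMC access to trial data generally, including by arm, not only to AEs and SAEs.
- Section 8.1 lets the responsible physician treat other events as serious, and lets the study physician stop enrollment on a judgment of participant safety.
- The case report forms and consent form are not in the documents and may hold further detail.
- Very few women are likely to be affected, and no between-arm test on them could be informative.

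Most of this stands, and it rules out a stronger reading. A reader might infer that fetal and newborn harm is always outside the AE and SAE definitions, that it can never reach the SMC, or that the undertaking in 4.1.4 cannot be kept. The documents do not support any of these. Fetal loss can enter as a maternal event, the discretionary routes exist, and a delivery after the last visit is not the same as a missing outcome.

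The narrower gap remains. The discretionary routes work only if someone learns of the event, and no time point, newborn assessment or listing ensures that. The SMC's general access helps only while its scheduled reviews continue.

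**Conclusion.** The point holds in limited form. The plan undertakes to record pregnancy outcome, but its AE and SAE definitions do not reach a birth defect or an illness confined to the newborn, and no visit item, reporting rule or analysis carries the outcome. Such an event may therefore miss the Day 29 SAE comparison and the SMC. This is more than missing detail, because applying the SAE rule as written leaves the event unclassified.

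The size is modest. The 23-week and 36-week thresholds rest on an assumed 280-day term and infusion on Day 1, and the percentages rest further on an even spread of gestational age. The expected number of pregnant participants is not stated and may be zero. The primary analysis and the sample size are untouched. The change is worth making because it is cheap and gives a stated safety undertaking a mechanism.

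**What to change.** 1. In 7.2, add congenital anomaly or serious neonatal illness in a participant's offspring to the SAE outcomes, and name fetal loss as a reportable event.
2. In 7.3.1, state that pregnancy outcome is obtained by chart review or phone at the end of pregnancy, even after Day 120. Complete the unfinished sentence on post-study SAEs so that late events are reported.
3. Report these outcomes as a descriptive listing by arm, separate from the Day 29 comparison. Amend 7.4.1 so that the listing goes to the SMC even after enrollment closes.

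Item 1 alone would not be enough: late births would still fall outside the Day 29 count and after the last scheduled SMC review. A listing is preferable to a test because the numbers will be so small.

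The cost is a few lines of text, one CRF page, one contact or chart check per pregnant participant, any permission needed to use newborn records, and a late listing for the SMC. A few outcomes will arrive well after the other data. Eligibility, treatment and the efficacy analysis do not change.
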